8.2 Safety Variables

8.2.1 Adverse Events

8.2.1.1 Adverse Events (AE) and Serious Adverse Events (SAE)

An adverse event is any untoward medical occurrence in a subject participating in a clinical trial. An adverse event can be any unfavorable and unintended sign, symptom or disease temporally associated with the use of the study medication, whether or not considered related to the study medication. Adverse events will be collected from the start of treatment until 30 days following the final visit dose. Any events occurring prior to treatment will be recorded on the medical history page with the event name and onset date and end date if not continuing. Pre-existing, known clinically significant conditions observed at screening should be recorded as medical history.

This definition also includes accidental injuries, reasons for any change in medication (drug and/or dose) other than planned titration, reasons for admission to a hospital, or reasons for surgical procedures (unless for minor elective surgery for a pre-existing condition). It also includes adverse events commonly observed and adverse events anticipated based on the pharmacological effect of the study medication. Any laboratory abnormality assessed as clinically significant by the Investigator must be recorded as an adverse event.

A treatment-emergent adverse event (TEAE) is any adverse event occurring after start of study medication and within the time of residual drug effect, or a pre-treatment adverse event or pre-existing medical condition that worsens in intensity after start of study medication and within the time of residual drug effect.

Adverse events should be recorded as diagnoses, if available. If not, separate sign(s) and symptom(s) are to be recorded. One diagnosis/symptom should be entered per record.

Note that death is not an event, but the cause of death is. An exception is the event of sudden death of unknown cause. Note that hospitalization is not an event; however, the reason for hospitalization is. Procedures are not events; the reasons for conducting the procedures are. In general, only the reason for conducting the procedure will be captured as an adverse event. However, if deemed necessary by the Investigator, a procedure can be captured along with the reason for conducting the procedure.

An overdose or medication error is not an adverse event unless it is temporally associated with an unfavorable or unintended sign or symptom.

Each adverse event is to be classified by the Investigator as serious or non-serious. A serious adverse event (SAE) is any untoward medical occurrence or effect that occurs at any dose:

- Results in death
- Is life-threatening (i.e., an immediate risk of death)
- Requires in-patient hospitalization or prolongation of existing hospitalization

- Results in persistent or significant disability/incapacity
- Is associated with a congenital anomaly/birth defect
- Is an important medical event

An adverse event caused by an overdose or medication error is considered serious if a criterion listed in the definition above is fulfilled.

Important adverse events that may not result in death, may not be life-threatening, or do not require hospitalization may be considered serious when, based on appropriate medical judgment, they may jeopardize the subject's safety or may require medical or surgical intervention to prevent one of the outcomes listed above.

Serious adverse events also include any other event that the Investigator or Sponsor judges to be serious or which is defined as serious by the regulatory agency.

The Investigator is to report all directly observed adverse events and all adverse events spontaneously reported by the trial subject using concise medical terminology. In addition, each trial subject will be questioned about adverse events. The question asked will be "Since you began taking the study medication, have you had any health problems?"

8.2.1.2 Procedures for Assessing, Recording, and Reporting Adverse Events and Serious Adverse Events

Throughout the duration of the study, the Investigator will closely monitor each subject for evidence of drug intolerance and for the development of clinical or laboratory evidence of adverse events. All adverse events (expected or unexpected) that occur during the course of the study, whether observed by the Investigator or by the subject, and whether or not thought to be drug-related, will be reported and followed until resolution or until they become stable.

The description of the adverse event will include description of event, start date, stop date, intensity, if it was serious, relationship to test drug, change in test drug dosage, if the subject died, and if treatment was required.

Adverse events will be coded to one of the following intensity categories below:

Severity	Definition
Mild	Awareness of signs or symptoms, but no disruption of usual activity
Moderate	Event sufficient to affect usual activity (disturbing)
Severe	Event causes inability to work or perform usual activities (unacceptable)

Adverse events will be coded into one of the following causality categories as defined below:

Category	Definition
Unrelated	Clearly and incontrovertibly due only to extraneous causes, and does not meet criteria listed under possible or probable.
Unlikely	Does not follow a reasonable temporal sequence from administration. May have been produced by the subject's clinical state or by environmental factors or other therapies administered.
Possible	Follows a reasonable temporal sequence from administration, but may have been also produced by the subject's clinical state, environmental factors, or other therapies administered.
Probable	Clear-cut temporal association with administration with improvement on cessation of investigational medicinal product or reduction in dose. Reappears upon rechallenge. Follows a known pattern of response to the investigational medicinal product.

Adverse events with the causality assessed as unrelated or unlikely are categorized as not related to study medication.

Adverse events with the causality assessed as possible or probable are categorized as related to study medication and are called adverse drug reactions.

All SAEs must be reported **immediately (no more than 24 hours after becoming aware of the event)**. The Investigator must complete the eCRF SAE Report according to the Serious Adverse Event Report Form Instructions.

8.2.2 Clinical Laboratory

The following laboratory tests will be analyzed locally by standard laboratory procedures:

- Hematology: complete blood count, total white blood cell count, differential count (neutrophils, lymphocytes, monocytes, eosinophils and basophils), red blood cells (hemoglobin, hematocrit, mean corpuscular volume, mean corpuscular hemoglobin and mean corpuscular hemoglobin concentration), platelets and reticulocytes.
- Biochemistry: sodium, potassium, glucose, blood urea nitrogen, creatinine, calcium, phosphate (inorganic), uric acid, total protein, albumin, bilirubin (total), alkaline phosphatase, aspartate transaminase, alanine transaminase, gamma-glutamyl transferase, and lactate dehydrogenase, iron, activated AST (GOT), activated ALT(GPT), LDH, cholesterol, HDL cholesterol, C-reactive protein, TIBC.
- Endocrinology: Ferritin, Vitamin D.
- Urinalysis: presence of glucose, ketones, protein, and leukocytes

8.2.3 Vital Signs

Vital signs measurements will include systolic/diastolic blood pressure, pulse rate, temperature, and respiratory rate.

8.2.4 Physical Examination

Physical examination will include assessment of standard body systems.

8.3 Immunogenicity

Anti-taliglucerase alfa antibodies, including neutralizing antibodies in subjects having a positive antibody response, will be assessed using a validated analytical method by a central laboratory.

9. STUDY PROCEDURES AND FLOW CHART

9.1 Study Flow Chart

Table 1: Study Flow Chart

Activity	Visit 0 Screening	Visit 1 Baseline	Visits 2-5	Visit 6	Visit 7 Month 3	Visits 8-13	Visit 14 Month 6	Visits 15-19	Visit 20 Month 9	Visits 21-26	Visit 27 Month 12
	Day -50 ±10	Day 1	Weeks 2, 4, 6, 8, (±3 days)	Week 10 (±3 days)	Week 12 (±7 days)	Weeks 14, 16, 18, 20, 22, 24 (±3 days)	Week 26 (±7 days)	Weeks 28, 30, 32, 34, 36 (±3 days)	Week 38 (±7 days)	Weeks 40, 42, 44, 46, 48, 50 (±3 days)	Week 52 ^d (±7 days)
Sign informed consent	X										
Review inclusion/exclusion criteria	X										
Demographics	X										
Medical history	X										
Current/concomitant medications	X	X	X	X	X	X	X	X	X	X	
Weight/height	X	X			X		X		X		X
Physical examination	X	X			X		X		X		X
Neurologic assessment	X						X				X
Hematology	X	X			X		X		X		X
Biochemistry ^{f,g}	X	X			X		X		X		X
Urinalysis	X	X			X		X		X		X
Serology (HIV, HBsAg, HCV)	X										
TSH, free T4, transferrin, B ₁₂ and folic acid	X										
Beta HCG (post-menarcheal girls)	X										
Vital signs ^h	X	X	X	X	X	X	X	X	X	X	
Anti-taliglucerase alfa antibodies		X				X					X
Organ volumes (MRI)	X										X
Ultrasound (liver and spleen)	X						X				X
Echocardiography	X										
Tanner Stage		X									X
X-ray of left hand and wrist		X									X
DEXA		X									X
mSST	X						X				X
Molecular analysis ^e	X										
Lyso-Gb1 biomarker		X			X		X		X		X
Chitotriosidase		X			X		X		X		X
IV infusion of taliglucerase alfa		X ^a	X ^b	X	X ^c	X	X ^c	X	X ^c	X	X ^c
Observe subject clinically		X	X		X		X		X		X
Evaluate injection site		X	X		X		X		X		X
Adverse events	X	X	X	X	X	X	X	X	X	X	X

DEXA = dual-emission X-ray absorptiometry; HBsAg = hepatitis B surface antigen; HCG = human chorionic gonadotropin; HCV = hepatitis C virus; HIV = human immunodeficiency virus, IV = intravenous; MRI = magnetic resonance imaging; T4 = thyroxine; TSH = thyroid stimulating hormone

- ^a A follow-up telephone call with the subject and/or parent or guardian will be held the day after the infusion.
- ^b Subjects who tolerate the infusions will be eligible for transfer to home or infusion center treatment after this visit at the discretion of the Investigator and Medical Monitor.
- ^c Taliglucerase alfa infusion must be done at the subject's selected medical center.
- ^d All Month 12 (Week 52) procedures/assessments are to be done for any subject who withdraws or is discontinued from the study before completion.
- ^e Molecular analysis will be done locally (if not done before), and a confirmation from Central Laboratory (Centogene) will be done using the CentoCard.
- ^f HDL, Phosphate inorganic and cholesterol assessments, which are taken at screening, should not be repeated at baseline, if done within a period of 1 month.
- ^g ALT and AST assessments are enough if activated ALT and activated AST are done on site (or the way around).
- ^h Vital signs to be done once on screening visit, from baseline till visit 27; to be done only pre and post infusion, and as needed if an AE occurs during infusion.

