6.3.3 Removal of Subjects from Study

Reasons for permanent discontinuation include the following:

1. The subject experiences two or more Grade 3 toxicities or one or more Grade 4 toxicity considered by the Investigator associated with taliglucerase alfa treatment (see [Section 8.2.1: Adverse Events](#); and [Appendix 14.5: WHO Common Toxicity Criteria](#))
2. The subject experiences progressive hypersensitivity or severe hypersensitivity will be treated appropriately and may be withdrawn from the study, at the discretion of the treating Investigator and/or Medical Monitor (see [Appendix 14.2: Infusion Rate Algorithm](#); and [Appendix 14.3: Taliglucerase Alfa Hypersensitivity Evaluation and Treatment Algorithm](#))
3. The subject, or subject's parent or guardian, requests to discontinue treatment
4. Investigator feels that it is not in the best interest of the subject to continue treatment and/or the Investigator believes that the subject can no longer be compliant with the requirements of the study
5. Deteriorating clinical condition, which the Investigator decides additional treatments would be needed

For any discontinuation, the Investigator will obtain all required details and document the date and the main reason for the premature discontinuation. If the reason for discontinuation is an adverse event, the specific event or the main laboratory abnormality will be recorded in the case report form (CRF). The Investigator will make thorough efforts to document the outcome. The Investigator will attempt to continue to follow the subject for the full duration of the study or at least for 30 days following discontinuation. If circumstances prevent the subject from completing all visits, every attempt will be made to complete all procedures listed in [Section 9.2.11](#) for Visit 27.

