6. DEXA
7. Taliglucerase alfa infusion
8. Adverse event evaluation

The following procedures will be performed after taliglucerase alfa dosing:

1. Observe the subject clinically for a minimum of 1 hour post-dosing.
2. Evaluate vital signs pre and post infusion, and as needed if an AE occurs during infusion. Evaluate the injection site.
3. A follow up telephone call with the subject and/or parent or guardian will be held the day after the infusion.

The subject and/or parent or guardian will be reminded of the date of the next visit.

9.2.3 Visits 2 – 5 (Weeks 2, 4, 6, and 8 ± 3 Days)

Subjects will receive their taliglucerase alfa infusion at their selected medical center. The following procedures will be performed post-dosing:

1. Observe the subject clinically for a minimum of 1 hour post-dosing.
2. Evaluate vital signs pre and post infusion, and as needed if an AE occurs during infusion.
3. Evaluate the injection site.

Adverse events and concomitant medications will be recorded at each visit.

Subjects will only receive transfusions at the medical center where they will be followed up and treated. The procedures to be followed will depend on local standards of care and procedures established at the medical center. Minimally, safety data (vital signs, adverse events, concomitant medications) will be recorded at each bi-weekly treatment with taliglucerase alfa administered at the medical center.

The subject and/or parent or guardian will be reminded of the date of the next visit.

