9.2.11 Visit 27 (Month 12 [Week 52] ± 7 Days)

All subjects are required to return to their selected medical center to receive their taliglucerase alfa infusion and have the following evaluations:

1. Physical examination including body weight and height.
2. Neurologic assessment.
3. MRI for spleen and liver volume.
4. Ultrasound for spleen and liver volume.
5. Clinical laboratory tests

- Hematology
- Biochemistry
- Urinalysis
- Biomarkers: Lyso-Gb1 and Chitotriosidase
- Anti-taliglucerase antibody test

6. Left hand and wrist X-ray for bone age
7. Tanner Stage

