9.2.12 Early Termination Visit

If the subject withdraws or is discontinued from the study before completion, the reason for discontinuation must be documented in the subject's CRF. Whenever a subject is discontinued, the procedures/assessments listed in [Section 9.2.11](#) should be conducted, unless advised otherwise by the Medical Monitor.

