14.3 Appendix 3: Taliglucerase Alfa Hypersensitivity Evaluation and Treatment Algorithm

During and after infusion of taliglucerase alfa, the following algorithm will be followed to monitor and manage the occurrence of hypersensitivity, anaphylaxis, or anaphylactoid reactions.

Clinical Signs

Early

- Sensations of warmth and itching
- Feelings of anxiety or panic

Moderate

- Pruritus
- Flushing
- Urticaria
- Chest discomfort
- Mild hypotension

Progressive

- Erythematous or massive urticarial rash
- Edema of face, neck, soft tissues

Severe

- Hypotension
- Bronchospasm (wheezing)
- Laryngeal edema (dyspnea, stridor, aphonia, drooling)
- Arrhythmias

Treatment Algorithm

With the onset of any of the above clinical signs, immediately discontinue study medication administration and initiate the following monitoring:

- Continuous electrocardiographic monitoring
- Continuous pulse oximetry
- Measure blood pressure every 5 minutes
- Perform chest auscultation every 5 minutes

- Blood samples need to be collected for Tryptase (29-33) and antibodies. Tryptase samples need to be withdrawn at:
 - 1st sample taken 0.25-3 hours after onset of symptoms
 - 2nd sample taken between 3-6 hours
 - 3rd sample taken 24-48 hours to verify the return to baseline

In the case of progressive or severe hypersensitivity, treat appropriately and withdraw the subject from the study. Treat as detailed below.

Urticaria or edema of the face, neck, or soft tissues

- Epinephrine 1:1000 solution, 0.5 mL subcutaneously, repeat as needed every 5-10 minutes
- Antihistamines
- Corticosteroids

Hypotension (systolic blood pressure (SBP) \leq 90 mmHg)

- Isotonic sodium chloride solution, 1 L every 30 minutes as needed to maintain SBP >90 mmHg
- Epinephrine 1:10,000 solution given IV at 1 μ g/minute initially, then 2-10 μ g/minute to maintain SBP >90 mmHg
- Norepinephrine 4 mg in 1 L 5% dextrose in water given IV at 2-12 μ g/minute to maintain SBP >90 mmHg
- Glucagon 1 mg in 1 L 5% dextrose in water given IV at 5-15 μ g/minute for refractory hypotension

Bronchospasm

- Oxygen by face mask at 6-8 L/minute to maintain oxygen saturation at $>90\%$
- Epinephrine 1:1000 solution, 0.5 mL subcutaneously
- Albuterol 0.5 mL of 0.5% solution in 2.5 mL of sterile saline every 15 minutes up to three doses
- Inhaled beta-agonists
- Corticosteroids

Laryngeal edema

- Epinephrine 1:1000 solution, 0.5 mL subcutaneously, repeat as needed every 5 to 10 minutes
- Corticosteroids

Premedication

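### Flow-chart footnote d, read literally, puts a taliglucerase alfa infusion into every early termination visit, in conflict with the discontinuation rules in Section 6.3.3 and Appendix 14.3

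*Protocol*

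**What the plan says.** Four parts of the protocol bear on the visit made by a subject who leaves early.

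- **Section 9.1, Table 1.** Footnote d is attached to the Week 52 column: "All Month 12 (Week 52) procedures/assessments are to be done for any subject who withdraws or is discontinued from the study before completion". That column marks the row "IV infusion of taliglucerase alfa", with footnote c: "Taliglucerase alfa infusion must be done at the subject's selected medical center". It also marks clinical observation and injection-site evaluation.
- **Section 9.2.11 (Visit 27).** The lead-in reads: "All subjects are required to return to their selected medical center to receive their taliglucerase alfa infusion and have the following evaluations". Eleven numbered evaluations follow, none of them an infusion, and then three post-dosing steps.
- **Section 9.2.12 (Early Termination Visit).** For a discontinued subject, the procedures and assessments listed in Section 9.2.11 "should be conducted, unless advised otherwise by the Medical Monitor".
- **Section 6.3.3 (Removal of Subjects).** The reasons for permanent discontinuation include "The subject experiences two or more Grade 3 toxicities or one or more Grade 4 toxicity considered by the Investigator associated with taliglucerase alfa treatment", and a request by the subject, parent or guardian to stop treatment. For progressive or severe hypersensitivity, withdrawal is left to the discretion of the Investigator and/or Medical Monitor. If a subject cannot complete all visits, sites are to try to complete every procedure listed in Section 9.2.11.

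Appendix 14.3 is directive on hypersensitivity: "In the case of progressive or severe hypersensitivity, treat appropriately and withdraw the subject from the study".

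**The concern.** Footnote d is the flow-chart instruction for subjects who leave early, and it is the only one of the three exit-visit instructions that is both unconditional and tied to a column in which the infusion is a marked activity. A site that follows it to the letter would infuse at exit a subject who was removed because of a reaction to the drug, or whose family had asked for treatment to stop. No legible text exempts those subjects. What is at stake is subject safety and a protocol that contradicts itself on dosing after discontinuation.

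Two further gaps follow if the infusion is not given at exit.

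- Footnote h ties vital signs from baseline to Visit 27 to before and after infusion (or to an adverse event during infusion), so no exit vital signs are defined for an undosed subject.
- Protocol Section 8.2.1.1 and SAP Section 3.5.1 run adverse-event collection to 30 days after the dose at the final visit. The end date is undefined for a subject who has no such dose.

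**Working it through.** The plan states no figure on this point, so the main check is a side-by-side reading.

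**Is the infusion part of the early termination visit?**

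1. *Footnote d with Table 1:* yes, without exception. The infusion is a row in the table, is marked in the Month 12 column, and footnote d covers all procedures and assessments of that visit. The protocol elsewhere treats the infusion as a procedure: in Section 9.2.2, "Taliglucerase alfa infusion" is item 7 of the procedures for Visit 1.
2. *Section 9.2.12 with 9.2.11:* unclear, and waivable. Section 9.2.12 invokes what Section 9.2.11 lists. The infusion is in the lead-in and not in the list, but the post-dosing steps assume that a dose was given. The Medical Monitor may advise otherwise.
3. *Section 6.3.3, closing sentence:* the same ambiguity, without the Medical Monitor exception, and in a section about permanent discontinuation.
4. *Appendix 14.3:* after progressive or severe hypersensitivity the subject is withdrawn. No exit dose is mentioned.

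Item 1 conflicts with item 4 and with the toxicity and subject-request reasons in Section 6.3.3. Items 2 and 3 do not resolve the conflict.

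**Is withdrawal for hypersensitivity mandatory?** Section 6.3.3 makes it discretionary and Appendix 14.3 directs it, for the same two categories of reaction (progressive or severe).

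**How many subjects might be concerned?** The documents give a discontinuation rate for hypersensitivity only. Inputs:

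- 2 of 32 adults discontinued for hypersensitivity (Protocol Section 4.3.1, Study PB-06-001).
- 9 evaluable subjects are needed and up to 15 are enrolled (Synopsis).

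Expected number = rate × n, and chance of at least one = 1 − (1 − rate)^n:

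- n = 9: 2/32 × 9 = 0.56, about 0.6; 1 − (30/32)^9 = 44%.
- n = 15: 2/32 × 15 = 0.94, about 0.9; 1 − (30/32)^15 = 62%.

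As a range, Section 6.2 of the appended label can be read as three hypersensitivity discontinuations among 32 treatment-naïve adults: two who developed antibodies on treatment, and one positive at baseline who withdrew. That gives 3/32 × 9 = 0.8 and 3/32 × 15 = 1.4.

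**The case against.** The strongest reply is that the protocol, read as a whole, does not order an infusion at exit. The section that governs the visit, 9.2.12, lets the Medical Monitor advise otherwise. Sections 9.2.12 and 6.3.3 point to what Section 9.2.11 lists, and the infusion is not in the numbered list. The post-dosing steps can be read as applying only if a dose is given. Section 6.3.3 speaks of permanent discontinuation and of follow-up for at least 30 days afterwards, which suggests that treatment has ended. Few investigators would infuse after a severe reaction.

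Much of this stands. A reader might infer that the early termination rule as a whole requires re-dosing of subjects removed for toxicity; the documents do not support that, for the reasons just given. What remains is that footnote d carries no exception, the waiver in Section 9.2.12 needs someone to intervene, and nothing legible settles whether the infusion is included. Monitors verify adherence to the protocol (Section 11.2), so a site that omits the infusion departs from footnote d's wording.

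Two other stronger readings also fail.

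- A reader might apply the appended label's 21 of 72 (29%) with hypersensitivity reactions, giving 21/72 × 9 = 2.6 or 21/72 × 15 = 4.4 subjects. That rate counts all reactions, not discontinuations. The label reports that both reacting pediatric patients and both reacting switch patients continued treatment.
- A reader might infer that an exit infusion disturbs the Month 12 imputation. SAP Section 5.3 uses the measurements obtained at the early termination visit whether or not a dose is given, and SAP Section 2.1.1 includes data after discontinuation.

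One limit: the diagram in Appendix 14.2 is not shown in the text reviewed, so a relevant stopping instruction there cannot be ruled out.

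**Conclusion.** The point holds as an internal contradiction with a safety consequence. Footnote d is unconditional and takes in the infusion, Section 9.2.12 is conditional, and Section 9.2.11 is ambiguous. A literal reading of footnote d cannot be squared with Section 6.3.3 or Appendix 14.3, and those two disagree with each other on hypersensitivity withdrawal.

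The expected number of subjects is small: about 0.6 of 9 or 0.9 of 15 for hypersensitivity discontinuations, or up to 0.8 and 1.4 on the higher reading. These figures assume that a rate from adults with Type 1 disease treated for 9 months carries over to Type 3 subjects of any age treated for 12 months. They do not cover removals for other drug toxicity or at the subject's request, for which the documents give no usable rate. The case for acting rests on the contradiction and its consequence for an individual subject, not on the count. The efficacy analysis is not affected.

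**What to change.** Reconcile Table 1 (footnotes d and h and the Visit 27 column), Sections 6.3.3, 9.2.11 and 9.2.12, and Appendix 14.3.

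- In Section 9.2.11 and the Visit 27 column, separate assessments from dosing-related items (infusion, post-dose observation, injection-site evaluation).
- In footnote d, Section 9.2.12 and the closing sentence of Section 6.3.3, state in the same terms which items apply at the early termination visit, and whether this depends on the reason for leaving.
- State whether vital signs are taken at an exit visit without an infusion, since footnote h links them to dosing.
- In Protocol Section 8.2.1.1 and SAP Section 3.5.1, define when the adverse-event period ends for a subject not dosed at exit.
- Make Section 6.3.3 and Appendix 14.3 agree on whether withdrawal after progressive or severe hypersensitivity is discretionary.

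The sponsor's medical lead decides the clinical rule; none is proposed here. The cost is a wording amendment with its ethics committee review, a matching line in the SAP, and no extra visits, procedures or subjects.
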